**Ain Shams University, Egypt**

**03-December- 2023**

## What is already known on this subject? AND What does this study add?

Refractive errors are associated with changes in angle kappa and corneal back elevation at the thinnest point in Pentacam.

The purpose of this study is to track:

The effect of anterior corneal astigmatism treatment on angle kappa and corneal back elevation.

## 1. INTRODUCTION/ REVIEW

Astigmatism has a corneal component and a lenticular component. Corneal astigmatism occurs when there are differences in the radius of curvature of the cornea in different meridians. ([Morlet et al, 2002](#)).

Astigmatism is classified as “with the rule” when the steep meridian on the corneal surface is between 60 and 120 degrees, and as “against the rule” when the steep meridian on the corneal surface is between 0 and 30 degrees or between 150 and 180 degrees. As the dioptric power of the posterior corneal surface is negative, posterior corneal astigmatism is classified as “with the rule” when the steep meridian on the corneal surface is between 0 and 30 degrees or between 150 and 180 degrees, and as “against the rule” when the steep meridian on the corneal surface is between 60 and 120 degrees. ([Koch et al, 2013](#)).

The magnitude of corneal astigmatism has been reported to vary with age. ([Attebo et al, 1999](#)). There is a shift of the steepest corneal meridian from the vertical (with-the-rule) to the horizontal meridian (against-the-rule). ([Mohammadi et al, 2016](#)).

The mean percentage and magnitude of astigmatism in the population aged 15

to 65 years are:  $\geq 0.5$  diopter (D) in 73.53%,  $\geq 1.0$  D in 32.78%,  $\geq 1.5$  D in 13.55%,  $\geq 2.0$  D in 6.86% and  $\geq 3.0$  D in 2.47%. (Gabor et al, 2013)

Angle kappa represents the angle between the visual and pupillary axes (Park et al, 2012). The visual axis connects the fovea with the fixation point and passes by the nodal point. The pupillary axis is the line passing through the center of the pupil perpendicular to the cornea. Angle kappa can be classified as positive (nasal) or negative (temporal). A positive angle kappa of  $5.0^\circ$  on average is generally found in the normal human eye. (Yeo et al, 2012).

Angle kappa decreases with age and tends to be larger in emmetropes and hypermetropes than in myopes). (Hashemi et al, 2010). But the relation of astigmatism to angle kappa still needs further studies. (Larysa et al, 2021).

Angle kappa is a crucial parameter in some surgical decisions. In keratorefractive surgery with a large angle kappa, there is a greater chance of decentration of ablation zones, and it may lead to negative visual effects such as high-order aberrations and under-correction. (Harrer et al, 2017 )

Angle kappa is a crucial parameter for proper centration of multifocal intraocular lens implantation. (Prakash et al, 2011)

Higher angle kappa values have been recorded in exotropic patients when compared to esotropic patients. Ophthalmologists must take the kappa angle into account when performing a Hirschberg or Krimsky test in young and uncooperative patients in order to improve surgical results. (Niamh Stone et al, 2009)

The exact angle kappa is classically measured using a synoptophore. (Park, et al.2012). Newer instruments measuring angle kappa are applied in clinical practice such as Orbscan, OPD scan, and Pentacam. (Garzon et al, 2020)

The Pentacam system is a rotating Scheimpflug-based instrument that obtains a three-dimensional model of the anterior segment of the eye which indicates an

image from the anterior corneal surface to the posterior lens surface. The device captures up to 25 slit images of the anterior segment of the eye by a 360-degree rotating Scheimpflug camera, collecting 25, 000 true elevation data points (respecting 500 true elevation points per slit image) within 2 seconds. ([Chen and Lam, 2009](#)).

Elevation-based corneal imaging techniques provide valuable information about the posterior corneal surface elevation properties which important in the preoperative examination of refractive surgery, average elevation values For normal eyes, at the posterior apex and thinnest points were  $0.8 \pm 3.0 \mu\text{m}$  (SD) and  $3.6 \pm 4.7 \mu\text{m}$ , respectively. ([Koch et al, 2012](#)).

Pentacam measures angle kappa by measuring the distance between the pupil center and the first Purkinje image. ([Garzon et al, 2020](#))

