## 2. AIM/ OBJECTIVES :

The exact relation between anterior corneal astigmatism and angle kappa is still not scientifically understood.

The objectives of this study are to study:

The effect of treating astigmatism on angle kappa and corneal back elevation.

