#### • **Study Procedures**

All patients will be scanned by OCULUS Pentacam® HR, Germany and all of them will be subjected to topography-guided femto-Lasik using the FS200 (Alcon Wavelight, Erlangen, Germany) and EX500 devices (Alcon Wavelight, Erlangen, Germany). And all of them will be done by one surgeon.

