#### • **Study Interventions**

All of them will undergo a complete ophthalmic examination to include or exclude cases, examinations including uncorrected distance visual acuity (UDVA) and corrected distance visual acuity (CDVA), IOP measurement, slit lamp examination, fundus examination, and Pentacam tomography.

At least 5 Pentacam scans will be taken for every patient each time. All Pentacam images will be collected and analyzed to measure the horizontal angle kappa, anterior astigmatism and its axis, back elevation data at the thinnest point, Anterior chamber depth and Axial length.

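### Angle kappa is defined as an angle but recorded as a distance, and the surgery alters the link between them, so a change or lack of change in the distance does not by itself show what happened to the angle

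*Protocol*

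**What the plan says.** Section 1 (Introduction/Review) of the protocol gives a geometric definition: "Angle kappa represents the angle between the visual and pupillary axes". It ties one of the two axes to the corneal surface: "The pupillary axis is the line passing through the center of the pupil perpendicular to the cornea". The typical value that follows, 5.0 degrees, is in angular units.

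Later in the same section the device's measurement is described as a length: "Pentacam measures angle kappa by measuring the distance between the pupil center and the first Purkinje image". The section sets this beside a reference method that the study does not use: "The exact angle kappa is classically measured using a synoptophore".

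Section 2 (Aim/Objectives) states the objective: "The effect of treating astigmatism on angle kappa and corneal back elevation". Under Study Interventions in section 3, the outcome comes from the device: "All Pentacam images will be collected and analyzed to measure the horizontal angle kappa". No unit is given there, and nothing says whether or how a distance becomes an angle. Under Study Procedures, "all of them will be subjected to topography-guided femto-Lasik". The inclusion criteria allow myopia up to 8 D and corneal astigmatism up to 5 D.

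**The concern.** An angle and a distance can stand in for one another while the factor linking them is fixed. In an unoperated eye, calling the distance angle kappa would be loose wording and little more. Here the objective implies a comparison before and after an operation that reshapes the surface producing the Purkinje reflex, so the linking factor itself differs between the two measurements.

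What is at stake is the headline conclusion. A report that treatment left angle kappa unchanged could be true of the distance and false of the angle that the protocol defines. The size of the discrepancy depends on how much the horizontal meridian is flattened, and so on sphere, cylinder and axis. Cylinder is also the variable that forms the two groups.

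**Working it through.** The protocol gives no figure to reproduce here. The check is geometric and starts from its own definitions.

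**Step 1: the link.** A line perpendicular to a locally spherical cornea passes through the centre of corneal curvature, so the pupillary axis joins that centre to the pupil centre. With coaxial fixation, the first Purkinje image lies on the fixation line through the same centre. Taking the fixation line as the visual axis:

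distance d = (R − e) × sin(kappa), so kappa = arcsin(d / (R − e)),

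where R is the anterior corneal radius in the horizontal meridian and e is the entrance-pupil depth.

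**Step 2: inputs.** From the protocol: correction up to 8 D of myopia and up to 5 D of astigmatism; average angle 5.0 degrees. Assumed, because the protocol gives none of them: R = 7.8 mm before surgery, e = 2.8 to 3.4 mm and unmoved by surgery, corneal index 1.376, and an illustrative distance of 0.30 mm.

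**Step 3: radius after D dioptres of horizontal flattening.** R′ = 376 / (376/7.8 − D), with 376/7.8 = 48.205.

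**Step 4: results.** Columns that depend on a single pupil depth use e = 3.0 mm.

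| Horizontal flattening | R (mm) | R − e (mm) | Rise in R − e, for e = 2.8 to 3.4 mm | Angle if d stays 0.30 mm | Distance if angle stays 5.0° |
|---|---|---|---|---|---|
| 0 D | 7.80 | 4.80 | none | 3.58° | 0.418 mm |
| 3 D | 8.32 | 5.32 | 10-12% | 3.23° | 0.463 mm |
| 5 D | 8.70 | 5.70 | 18-21% | 3.02° | 0.497 mm |
| 8 D | 9.35 | 6.35 | 31-35% | 2.71° | 0.554 mm |

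For an unchanged distance, the angle falls by a smaller percentage than the conversion length rises. The fall is about 9% at the low end (3 D, e = 2.8 mm: 1 − 5.00/5.52) and about 26% at the high end (8 D, e = 3.4 mm: 1 − 4.40/5.95).

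**Step 5: dependence on axis.** If 5 D of cylinder is flattened in the horizontal meridian, the 5 D row applies. If it is flattened in the vertical meridian alone, horizontal R does not change and the 0 D row applies. Sphere flattens both meridians.

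**Step 6: sensitivity.** A second calculation took R from 7.4 to 8.2 mm and anatomical pupil depth from 3.3 to 4.0 mm. It recomputed the entrance pupil from corneal power (posterior power −6 D) and allowed 0.013 mm of ablation per dioptre. The rise was about 4% at 1 D, 11-14% at 3 D, 20-24% at 5 D and 33-40% at 8 D. The direction was the same throughout, and the size slightly larger.

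**The case against.** The strongest reply is that the protocol discloses its operational definition. The introduction says what the device measures, the outcome is taken from that device, and no comparison with 5.0 degrees is planned. On this view only a loose term needs tidying. That would suffice for a cross-sectional study, but not when the linking factor changes between measurements.

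Several further objections stand and limit the point:

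- **The angle itself can move.** A reader might infer that any change in the distance is a mere artefact of scale and no change in angle kappa. The documents do not support that. The pupillary axis is defined as perpendicular to the cornea, so reshaping the cornea can change the angle itself. The fall from 3.58 to 2.71 degrees in the table would be a real effect under the protocol's definition.
- **What the arithmetic demonstrates.** The fixed-distance column shows a missed change. The reverse case, a larger distance with the same angle, requires the reflex or the pupil centre to shift. That depends on where the ablation is centred, which the protocol does not say.
- **Bias between groups.** A reader might also infer that the comparison of the two astigmatism groups is biased. That is possible but not shown. Sphere is corrected in both groups, no imbalance is documented, and cylinder treated mainly in the vertical meridian contributes almost nothing.
- **Sources of the figures.** The protocol states none of the optical constants.
- **Anterior chamber depth is not entrance-pupil depth.** In the second calculation, an anatomical depth of 3.6 mm with R = 7.8 mm gave an entrance-pupil depth of 3.04 mm, so a converted angle is approximate.

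**Conclusion.** The point holds in limited form and should be acted on. The mismatch between a defined angle and a recorded distance is explicit in the protocol. That surgery alters the link follows from the protocol's definitions and elementary geometry, and the direction held across all the radii and depths tried. Neither a change nor a lack of change in the distance, taken alone, settles what happened to the angle.

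Under the main assumptions the link shifts by roughly 10 to 35% for 3 to 8 D of horizontal flattening. It shifts by only about 4% at 1 D (second calculation) and by almost nothing when only the vertical meridian is flattened. The shift may differ between groups through cylinder, axis and sphere. Cancellation therefore cannot be assumed, but neither can a bias be claimed.

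**What to change.** In section 2 and under Study Interventions, name the outcome as the horizontal distance, in millimetres, from pupil centre to first Purkinje image, and limit the main conclusion to that distance. It should not be read against the 5.0 degree average.

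As a secondary analysis, convert each visit's distance to an angle with kappa = arcsin(d / (R − e)). Use that visit's own horizontal anterior radius and an entrance-pupil depth approximated from that visit's anterior chamber depth. State the approximation, show results over a range of e, and never apply one fixed factor to both visits. Report whether the two scales lead to the same conclusion.

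The cost is a wording change, one approximate derived variable and a narrower main conclusion. Anterior chamber depth is already on the list of measurements, and the horizontal radius should come from the same scans that supply anterior astigmatism and its axis. No extra visit or procedure is needed, and treatment is unaffected.

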## 2. AIM/ OBJECTIVES :

The exact relation between anterior corneal astigmatism and angle kappa is still not scientifically understood.

The objectives of this study are to study:

The effect of treating astigmatism on angle kappa and corneal back elevation.

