### *- Inclusion Criteria:*

- Subjects aged 21 – 45 years from both sexes.

- myopia up to -8 D
- Corneal astigmatism up to -5 D.
- Stable refraction for 1 year before surgery.
- No ectasia.
- Corneal thickness of more than 500  $\mu\text{m}$ .
- Calculated residual stromal bed of more than 300  $\mu\text{m}$ .
- Axial length up to 30 mm.

- Exclusion Criteria:

None of the patients enrolled have:

- History of previous ocular surgery.
- History of previous ocular trauma.
- Corneal opacities within the central 7 mm.
- Moderate to severe dry eye diseases.
- Active or previous diseases linked to the anterior segment of the eye.
- Active or previous diseases linked to the posterior segment of the eye.
- Diabetic patients.
- Patients with collagen vascular diseases.
- Patients with glaucoma.
- Patients with post-operative complications

• **Sample Size** (100 eyes) will be divided equally into 2 groups:

- Group 1: subjects have anterior corneal astigmatism of -1.5 to -5 D.
- Group 2: subjects have anterior corneal astigmatism below -1.5 D.

• **Ethical Considerations**

The study will be conducted in accordance with the ethical standards stated by the ethical committee in the Faculty of Medicine- Ain Shams University,

with informed consent.

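### The aim is the effect of treating astigmatism, but every eye gets the whole LASIK procedure, so a within-group pre-post change cannot be attributed to the astigmatic correction

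*Protocol*

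**What the plan says.** The opening section of the protocol (what is known and what the study adds) gives the purpose as "The effect of anterior corneal astigmatism treatment on angle kappa and corneal back elevation". Section 2, Aim/Objectives, gives the one objective as "The effect of treating astigmatism on angle kappa and corneal back elevation".

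Section 3 fixes the design:
- The study is prospective and observational.
- Myopia up to -8 D and corneal astigmatism up to -5 D are eligible.
- The 100 eyes are divided equally: "Group 1: subjects have anterior corneal astigmatism of -1.5 to -5 D" and "Group 2: subjects have anterior corneal astigmatism below -1.5 D". I read the second as smaller magnitude; on the signed scale it would overlap the first.
- Study Procedures gives every patient topography-guided femto-LASIK on the same platform, by one surgeon.
- Study Interventions lists what is taken from the Pentacam images: horizontal angle kappa, anterior astigmatism and axis, back elevation at the thinnest point, anterior chamber depth and axial length. Treated sphere and treated cylinder are not listed.
- Statistical Analysis names only the software.

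The protocol itself gives reason to think that refraction other than astigmatism matters. The opening section says "Refractive errors are associated with changes in angle kappa and corneal back elevation at the thinnest point in Pentacam", and the Introduction says "Angle kappa decreases with age and tends to be larger in emmetropes and hypermetropes than in myopes".

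**The concern.** The aim isolates one component of a procedure that the design delivers only as a package. Each eye receives a flap, whatever spherical ablation it needs and whatever astigmatic ablation it needs, in one session. If angle kappa or back elevation changes after surgery, the before-and-after difference cannot show which component caused it. A change due to the flap or to the myopic ablation could be published as an effect of astigmatism treatment.

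The only internal comparison that the protocol sets up is between two treated groups. It bears on astigmatism, because the amount of astigmatism corrected should differ between them. But it compares larger with smaller corrections, not treated with untreated eyes, and nothing holds treated sphere equal across the groups. A statistical analysis plan could add covariates. It could not supply a comparator, and it could not make a pre-post change answer the stated aim.

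**Working it through.** The protocol gives no effect size, SD, alpha or power for the 100 eyes, so there is no figure of its own to reproduce. The steps below test the attribution argument. Values marked as assumed are not in the documents.

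**1. What each comparison estimates.** Take an additive model for one eye:

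change = a + b × (sphere corrected) + c × (cylinder corrected),

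where a is the effect of the flap and the procedure in general. Set c = 0, so that astigmatism treatment does nothing.

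- *Pre-post change within a group:* a + b × mean sphere. With assumed a = 1 unit, b = 0.25 to 0.5 unit per D and mean sphere 4 D, this is 1 + 0.25 × 4 = 2.0 to 1 + 0.5 × 4 = 3.0 units. None of it comes from astigmatism.
- *Difference between groups:* a cancels, leaving b × (difference in mean sphere). This is 0 if sphere is balanced. If mean sphere differed by an assumed 2 D, it is ±0.5 to ±1.0 unit. The sign depends on which group has more myopia, which the protocol does not fix.

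**2. How often a paired test would mislead.** Inputs: 50 eyes per group (100 divided equally, Sample Size); two-sided 5% level (assumed); c = 0; eyes treated as independent (assumed). If the rest of the procedure shifts the outcome by d SDs of the within-eye change, the paired t statistic has 49 degrees of freedom, noncentrality d × √50 and critical value 2.01.

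| Assumed d | Noncentrality | Probability of significance |
|---|---|---|
| 0.2 | 1.41 | 28% |
| 0.3 | 2.12 | 55% |
| 0.5 | 3.54 | 93% |

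**3. What the cut at -1.5 D discards.** The Introduction gives population prevalences of 73.53%, 32.78%, 13.55%, 6.86% and 2.47% at or above 0.5, 1.0, 1.5, 2.0 and 3.0 D. Differences give the bins:

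- Group 1, from 13.55: 6.69 (1.5–2 D), 4.39 (2–3 D), 2.47 (over 3 D).
- Group 2, from 86.45: 26.47 (0–0.5 D), 40.75 (0.5–1 D), 19.23 (1–1.5 D).

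Assume values uniform within bins and a top bin ending at 4 D or 5 D. With equal groups:

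loss = W / (W + B), where W is the mean of the two within-group variances and B = (difference in means)² / 4.

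| Top bin ends at | Mean, Group 1 | Mean, Group 2 | W | B | Loss |
|---|---|---|---|---|---|
| 4 D | 2.31 D | 0.71 D | (0.477 + 0.151)/2 = 0.314 | 1.604²/4 = 0.643 | 33% |
| 5 D | 2.40 D | 0.71 D | (0.777 + 0.151)/2 = 0.464 | 1.695²/4 = 0.718 | 39% |

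With a front-loaded top bin the loss is 31% and 35%. These figures apply if group were the only exposure used and the relation with magnitude were linear.

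**The case against.** The strongest reply is that the protocol names no analysis. It commits to neither a pre-post test nor a crude group contrast, and covariates, continuous exposures and similar choices commonly sit in a statistical analysis plan. This stands: a reader might infer that the investigators intend to report pre-post change as the astigmatism effect, and the document does not say so. What remains is that the aim and the group structure are fixed here, and they do not match.

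A second reply is that the design is better than it looks. Group 2 has no lower limit, so it may contain eyes with almost no cylinder. On the Introduction's prevalences 26.47/86.45 = 31% of it would lie below 0.5 D. A common flap effect cancels between the groups, and a graded comparison is a reasonable approach in an observational study. This also stands, and it rules out the stronger reading that the study can say nothing about astigmatism. But these near-sphere-only eyes are not designated as a comparator, and the cut merges them with eyes just under 1.5 D.

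Third, a reader might infer that spherical correction has been shown to bias the group contrast. It has not. The protocol's statements about refractive error, refractive class and age are associations; they do not show that correcting sphere changes either outcome. The imbalance in treated sphere is unknown in size and direction, and could attenuate or inflate the contrast.

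Finally, since "Astigmatism has a corneal component and a lenticular component", one might infer that the groups are cut on the wrong quantity. The documents do not support that: the stated purpose and the group definitions both refer to anterior corneal astigmatism, so they agree.

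**Conclusion.** The point holds in a limited form. As designed, a within-group pre-post change is the effect of the whole procedure and cannot be reported as the effect of treating astigmatism. That follows from the text and needs no assumption about effect sizes. The 28%, 55% and 93% illustrate the consequence and depend on the assumed shifts.

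The two-group comparison is usable evidence on larger versus smaller corrections. Its weaknesses are the information lost by the cut and an uncontrolled difference in treated sphere. The loss of roughly a third (31–39%) applies general-population prevalences at ages 15 to 65 to surgical candidates aged 21 to 45, so it is an order of magnitude only. The sphere difference cannot be sized from the documents.

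This should be corrected before analysis, but it does not make the data unusable. Confidence is medium, because an analysis plan that is not shown may already address the adjustment.

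**What to change.** Choose one of two routes.

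1. *Reword the aim.* In the opening section and section 2, describe the change in angle kappa and back elevation after topography-guided femto-LASIK, by baseline anterior corneal astigmatism.
2. *Keep the aim and state the analysis that addresses it.* Retain the two groups for recruitment and description. Record treated sphere and treated cylinder for each eye. State that the astigmatism question is answered by regressing the post-operative outcome on treated cylinder kept continuous, adjusted for baseline outcome, treated sphere and age. Report the slope as an association per dioptre treated; without untreated eyes it is not a treated-versus-untreated effect. Planned rather than achieved correction is the safer exposure, because the Introduction says of a large angle kappa that "it may lead to negative visual effects such as high-order aberrations and under-correction", so achieved correction may itself depend on an outcome.

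Under either route, add a sentence that a within-group pre-post change will not be attributed to astigmatism treatment.

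The cost is protocol wording and, for the second route, two dataset columns and one regression that SPSS can run. The planned ablation must already be known, since eligibility requires a calculated residual stromal bed. Surgery, eligibility and recruitment are unchanged. The downside of the second route is a less simple summary than two group means.
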